1.2 Decitabine and Hypomethylating agents in AML/MDS

[REDACTED]	[REDACTED]	[REDACTED]	[REDACTED]	[REDACTED]
[REDACTED]	[REDACTED]	[REDACTED]	[REDACTED]	[REDACTED]
[REDACTED]	[REDACTED]	[REDACTED]	[REDACTED]	[REDACTED]
	[REDACTED]	[REDACTED]	[REDACTED]	[REDACTED]
	[REDACTED]	[REDACTED]	[REDACTED]	[REDACTED]
	[REDACTED]	[REDACTED]	[REDACTED]	[REDACTED]
[REDACTED]	[REDACTED]	[REDACTED]	[REDACTED]	[REDACTED]
	[REDACTED]	[REDACTED]	[REDACTED]	[REDACTED]
	[REDACTED]	[REDACTED]	[REDACTED]	[REDACTED]
[REDACTED]	[REDACTED]	[REDACTED]	[REDACTED]	[REDACTED]
[REDACTED]	[REDACTED]	[REDACTED]	[REDACTED]	[REDACTED]
[REDACTED]	[REDACTED]	[REDACTED]	[REDACTED]	[REDACTED]
[REDACTED]	[REDACTED]	[REDACTED]	[REDACTED]	[REDACTED]

[REDACTED]

[REDACTED]

[REDACTED]

[REDACTED]

[REDACTED]

[REDACTED]

[REDACTED]

[REDACTED]

[Redacted text]

[figure not shown]
[Redacted]	[Redacted]	[Redacted]
[Redacted]	[Redacted]	[Redacted]
[Redacted]	[Redacted]	[Redacted]
[Redacted]	[Redacted]	[Redacted]
[Redacted]	[Redacted]	[Redacted]
[Redacted]	[Redacted]	[Redacted]
[Redacted]	[Redacted]	[Redacted]
[Redacted]	[Redacted]	[Redacted]
[Redacted]	[Redacted]	[Redacted]
[Redacted]	[Redacted]	[Redacted]

[Redacted text]

[Redacted text]

[Redacted text]

[Redacted text]

1.3 Correlative Studies

With exception of the peripheral blood sample collected on Cycle 1 Day 4, all correlative studies will be collected under HRPO# 201011766 (“Tissue Acquisition for Analysis of Genetic Progression Factors in Hematologic Diseases”) that all patients will be concurrently enrolled in. The goals of the correlative studies include:

1. To correlate patient-specific mutations with response to decitabine.
We will perform exome sequencing of each patient’s pre-study bone marrow sample and skin sample. We will determine AML/MDS-associated variants found in the bone marrow, but not skin sample. We will correlate the presence of mutations with response (especially mutations in *DNMT3A*, *IDH1*, *IDH2*, and *TET2*). This study is powered to identify mutations with >80% sensitivity to predict decitabine response if used as a clinical assay.
2. To correlate the velocity and depth of response with response to decitabine.
We will assess tumor burden by allele frequency of patient-specific mutations in bone marrow samples collected pre study, Cycle 1 Day 10±1, Cycle 1 Day 28±4, and Cycle 2 Day 28±4. We will assess mutations in at least 24 recurrently mutated genes (including, but not limited to: *FLT3*, *DNMT3A*, *NPM1*, *TET2*, *WT1*, *IDH1*, *IDH2*, *RUNX1*, *NRAS*, *TP53*, *U2AF1*, *KRAS*, *PHF6*, *MSTP9*, *PTPN11*, *KIT*, *SMC3*, *PRUNE2*, *ETV6*, *CEBPA*, *SMC1A*, *ASXL1*, *STAG2*, *RAD21*) as well as all patient-specific mutations discovered during exome sequencing. The leukemic allele frequency will be measured using the Illumina MySeq or HiSeq platform using DNA capture by gene specific biotinylated-oligonucleotides. Patient bone marrow samples will be assessed pre-study, Cycle 1 Day 10 ± 1, Cycle 1 Day 28 ± 4, and Cycle 2 Day 28 ± 4 and compared with patient specific skin samples (normal control). The velocity of response will be calculated as the natural log rate of patient-specific mutation allele frequency clearance. Depth of response will be defined as the lowest patient-specific mutation

allele frequency in a bone marrow sample. The velocity and depth of tumor response will be correlated to:

- Achievement of clinical CR,
- Time to best response,
- Mutational status,
- Time to disease progression.

Because all patient-specific exome-discovered mutations will be assessed a second time in the primary bone marrow sample as well as the Cycle 1 Day 10 \pm 1, Cycle 1 Day 28 \pm 4, and Cycle 2 Day 28 \pm 4 bone marrow samples, this study will also serve to validate all exome-discovered mutations. This is important, because exome sequencing is associated with a 20-50% false-discovery rate depending on type I error tolerated (mutation-calling algorithms are typically set for greater sensitivity than specificity). Thus, many mutations discovered during exome sequencing are incorrect. This second analysis of these mutations will serve to exclude these false positive calls.

3. To correlate the bone marrow expression profile from pre-study and Cycle 1 Day 10 \pm 1 with response to decitabine.

We will correlate expression signatures, and changes in expression signatures, with:

- Achievement of clinical CR,
- Mutation status.

4. To correlate steady-state plasma decitabine concentration on Cycle 1 Day 4 \pm 1 with:

- Achievement of CR.

5. To correlate the extent of bone marrow DNA hypomethylation on Cycle 1 Day 10 \pm 1 with response to decitabine.

We will assess the percent reduction in bone marrow methylcytosine content using LC-MS. Patients will be evaluated pre-study and Cycle 1 Day 10 \pm 1. The change in DNA methylcytosine content will be correlated to:

- Achievement of clinical CR,
- Change in expression signature.

This will determine whether inadequate blast exposure to decitabine correlates with drug resistance.

2.0 OBJECTIVES

2.1 Primary Objective

To determine whether patient-specific mutations correlate with clinical overall response to decitabine in patients with AML or MDS.

2.2 Secondary Objectives

- To determine whether 10 consecutive days per cycle of decitabine improves outcomes compared with historical controls treated with 5 consecutive days per cycle of decitabine.
- To determine whether other biomarkers correlate with clinical overall response to decitabine in patients with AML or MDS. These will include:
 1. The velocity and depth of patient-specific mutation clearance;
 2. The bone marrow expression profile and change in expression profile during decitabine treatment;
 3. The steady-state plasma decitabine concentrations;
 4. The decrease in bone marrow methylcytosine content in response to decitabine.

3.0 PATIENT SELECTION

3.1 Inclusion Criteria

One of the following:

- Patient must have non-M3 AML and be ≥ 60 years of age OR
- non-M3 AML with relapsed disease OR
- Symptomatic MDS with one of the following:
 - Symptomatic anemia with either hemoglobin < 10.0 g/dL or requiring RBC transfusion
 - Thrombocytopenia with a history of two or more platelet counts $< 50,000$ /mCL or a significant hemorrhage requiring platelet transfusions
 - Neutropenia with two or more ANC $< 1,000$ /mCL

All of the following:

1. Patient must have an ECOG performance status ≤ 2 .
2. Patient must have $>10\%$ disease burden measured by cytomorphology, flow cytometry, or cytogenetics.
3. Patient must have peripheral white blood cell count $\leq 50,000$ /mcl.
4. Patient must have adequate organ function, defined as:
 - a. Total bilirubin ≤ 1.5 x ULN
 - b. AST/ALT ≤ 2.5 x ULN
 - c. Serum creatinine ≤ 2.0 x ULN
5. Patient must have undergone ≤ 2 cycles of prior hypomethylating agent (decitabine or azacitidine).
6. Patient must be enrolled in HRPO# 201011766 (“Tissue Acquisition for Analysis of Genetic Progression Factors in Hematologic Diseases”).
7. Patient must be ≥ 18 years of age.
8. Patient must be able to understand and willing to sign an IRB-approved written informed consent document.

3.2 Exclusion Criteria

1. Patient must not be pregnant or nursing.
2. Patient must not have known CNS leukemia.
3. Patient must not have a history of positive HIV serology.
4. Patient must not have a history of positive Hepatitis C serology.
5. Patient must not have undergone a prior allogeneic stem cell transplant.
6. Patient must not have any uncontrolled intercurrent illness including, but not limited to, ongoing or active infection, ongoing or active GVHD, congestive heart failure of NYHA class 3 or 4, unstable angina pectoris, cardiac arrhythmia, or psychiatric illness/social situation that would limit compliance with study requirements.
7. Patient must not have had radiation therapy within 14 days of enrollment.
8. Patient must not have received any chemotherapy within 21 days of enrollment, and any acute treatment-related toxicities must have returned to baseline. Patients

may be receiving hydra at time of enrollment.

3.3 Inclusion of Women and Minorities

Both men and women and members of all races and ethnic groups are eligible for this trial.

4.0 REGISTRATION PROCEDURES

Patients must not start any protocol intervention prior to registration through the Siteman Cancer Center.

The following steps must be taken before registering patients to this study:

1. Confirmation of patient eligibility by Washington University
2. Registration of patient in the Siteman Cancer Center database
3. Assignment of unique patient number (UPN)

Once the patient has been entered in the Siteman Cancer Center database, the WUSM coordinator will forward verification of enrollment and the UPN via email.

4.1 Confirmation of Patient Eligibility

Confirm patient eligibility collecting the information listed below and scanning and emailing it to the research coordinator listed in the *Siteman Cancer Center Clinical Trials Core Protocol Procedures for Secondary Sites* packet at least one business day prior to registering patient:

1. Your name and contact information (telephone number, fax number, and email address)
2. Your site PI's name, the registering MD's name, and your institution name
3. Patient's race, sex, and DOB
4. Three letters (or two letters and a dash) for the patient's initials
5. Currently approved protocol version date
6. Copy of signed consent form (patient name may be blacked out)
7. Planned date of enrollment
8. Completed eligibility checklist, signed and dated by a member of the study team
9. Copy of appropriate source documentation confirming patient eligibility

4.2 Patient Registration in the Siteman Cancer Center Database

Registrations may be submitted Monday through Friday between 8am and 5pm CT. Urgent late afternoon or early morning enrollments should be planned in advance and coordinated with the Washington University research coordinator. Registration will be confirmed by the research coordinator or his/her delegate by email within one business day. Verification of eligibility and registration should be kept in the patient chart.

All patients at all sites must be registered through the Siteman Cancer Center database at Washington University.

4.3 Assignment of UPN

Each patient will be identified with a unique patient number (UPN) for this study. Patients will also be identified by first, middle, and last initials. If the patient has no middle initial, a dash will be used on the case report forms (CRFs). All data will be recorded with this identification number on the appropriate CRFs.

5.0 INVESTIGATIONAL PLAN

5.1 Summary of Study Design

This is an open-label, single-arm, Phase II, biomarker study of patients with AML or MDS who are treated with 10 consecutive days of decitabine. FAB-M3 AML is excluded from this trial, because other well-tolerated options exist for the treatment of FAB-M3 acute promyelocytic leukemia. AML patients who are < 60 years old and have not received cytotoxic induction chemotherapy are also excluded, because cytotoxic therapy offers a curative possibility for these patients. MDS patients without cytopenias are also excluded because these patients can be followed with watchful-waiting.

All patients will undergo bone marrow biopsies pre-study, on Cycle 1 Day 10 ± 1, and on Day 28 ± 4 of Cycles 1, 2, 4, and 6. Following Cycle 6, bone marrow biopsies should be performed at the discretion of the treating physician to assess for relapse or progression. Patients will provide a skin biopsy sample pre-study. Patients will also provide peripheral blood samples on Cycle 1 Day 4 ± 1 for pharmacokinetic studies. See Section 8.0 for details on correlative studies.

Patients will receive decitabine 20 mg/m²/day as a 1-hour infusion on consecutive Days 1-10 in 28-day cycles. The dose will be calculated based on actual patient weight at the beginning of each cycle.

Once AML patients achieve morphologic complete remission with incomplete blood count recovery (CRi) or MDS patients achieve a marrow complete response (Marrow CR) as defined in Section 9.0, decitabine administration may be decreased to 20 mg/m²/day for ten consecutive days every 6 weeks, to limit myelosuppressive toxicity and improve count recovery. After 2 cycles at 6 week intervals, the dose may be reduce to 20 mg/m²/day for five consecutive days in 6 week cycles, at the discretion of the treating physician. After two cycles of five consecutive days of treatment, if the patient meets the definition of CR with complete cytogenetic response as defined in Section 9.0, administration may further be decreased to three consecutive days per cycle at the discretion of the treating physician.

It will be a logistical goal of this trial consistently to return preliminary exome results to the treating physician by the end of Cycle 1 and validated results by the end of Cycle 2. However, this logistical goal is not a primary or secondary aim of this study. Given the limited data regarding mutation presence and drug response, we do not anticipate that the results will directly influence therapeutic decisions made by the treating physician. However, the development of comprehensive genomic pipelines and integration of this data into a clinical trial setting will be required before personalized medicine can be realized.

5.2 Study Procedures

5.2.1 Pre-study Procedures

Pre-study procedures must take place no more than 14 days prior to the first dose of decitabine except where noted below.

1. Bone marrow aspirate and biopsy. Standard bone marrow procurement procedures will be followed for collection of the tissue. Assessments performed on bone marrow will include correlative studies (collected under HRPO# 201011766), morphologic assessment, cytogenetics, and FISH.
2. Bone marrow or peripheral blood for flow cytometry
3. Skin biopsy sample (collected under HRPO# 201011766). There is no required time frame for this sample; it may have been collected months or even years prior to the first dose of decitabine.

5.2.2 Baseline Evaluation

Baseline evaluations must take place no more than 7 days prior to the first dose of decitabine.

1. Medical history
2. Physical exam including height, weight, and ECOG performance score.
3. Record transfusion requirements for 8 weeks before first dose of study drug
4. CBC with differential and platelets
5. Serum chemistries, including bicarbonate, calcium, glucose, total protein, albumin, BUN, potassium, chloride, sodium, creatinine, total bilirubin, AST, ALT, alkaline phosphatase, LDH
6. Urine β HCG pregnancy test if appropriate

5.2.3 Day 1 of Each Cycle

1. Physical exam, including weight
2. CBC with differential and platelets
3. Serum chemistries, including bicarbonate, calcium, glucose, total protein, albumin, BUN, potassium, chloride, sodium, creatinine, total bilirubin, AST, ALT, alkaline phosphatase, LDH

5.2.4 Cycle 1 Days 1-10

Decitabine administration, 20 mg/m² per day given as a 1-hour continuous intravenous infusion. The dose will be calculated based on actual patient weight at the beginning of each cycle. Patients may be premedicated with lorazepam, prochlorperazine, palonosetron, or ondansetron at the treating physician's discretion.

5.2.5 Cycle 1 Day 4 ± 1

Obtain 3 mL peripheral blood for correlative studies. Sample must be obtained 45 minutes ± 15 minutes after beginning the infusion, before the decitabine infusion is complete, and should be obtained from the opposite arm as the infusion. The sample should be collected in a 3 mL K3EDTA tube pre-loaded with 8 mcL of tetrahydrouridine (THU 500 mcg/mL), an inhibitor of cytidine deaminase. The sample should be processed by the Tissue Procurement Core Facility at the Siteman Cancer Center. Plasma should be separated and stored per protocols.

5.2.6 Cycle 1 Day 10 ± 1

Bone marrow aspirate and biopsy. Standard bone marrow procurement procedures will be followed for collection of the tissue. Assessments performed on bone marrow will include correlative studies (collected under HRPO# 201011766), morphologic assessment, cytogenetics, and FISH.

5.2.7 Weekly

CBC with differential and platelets. After the first cycle, this may be changed to every other week at the discretion of the treating physician.

5.2.8 Every Other Week

Serum chemistries, including bicarbonate, calcium, glucose, total protein, albumin, BUN, potassium, chloride, sodium, creatinine, total bilirubin, AST, ALT, alkaline phosphatase, LDH. After the first cycle, this may be changed to every month at the discretion of the treating physician.

5.2.9 Cycles 1, 2, 4 and 6 Day 28 ± 4 days

Bone marrow aspirate and biopsy. Standard bone marrow procurement procedures will be followed for collection of the tissue. Assessments performed on bone marrow will include: correlative studies (collected under HRPO# 201011766), morphologic assessment, cytogenetics, and FISH.

Patients who achieve with clinical response (CRi or better) and are receiving cycles every 6 weeks, will undergo bone marrow biopsies on day 42 ± 4.

5.2.10 End-of-Study Procedures

1. Physical exam
2. CBC with differential and platelets.
3. Serum chemistries including bicarbonate, calcium, glucose, total protein, albumin, BUN, potassium, chloride, sodium, creatinine, total bilirubin, AST, ALT, alkaline phosphatase, and LDH.

4. Bone marrow aspirate and biopsy. Standard bone marrow procurement procedures will be followed for collection of the tissue. Assessments performed on bone marrow will include morphologic assessment, cytogenetics, and FISH.

5.2.11 Post-study Follow-up

Patients are to be followed according to standard patient care procedures for 30 days following the date of the last decitabine dose to monitor for toxicity, survival, and response. Thereafter, the investigator or designee will record information on subsequent therapy, disease progression, and/or death every 6 months for 2 years after last dose of study drug or until the patient is lost to follow-up or dies.

5.3 Duration of Therapy

If at any time the constraints of this protocol are considered to be detrimental to the patient's health and/or the patient no longer wishes to continue protocol therapy, the protocol therapy should be discontinued and the reason(s) for discontinuation documented in the case report forms.

In the absence of treatment delays due to adverse events, treatment may continue indefinitely or until one of the following criteria applies:

- Documented and confirmed disease progression
- Death
- Adverse event(s) that, in the judgment of the investigator, may cause severe or permanent harm or which rule out continuation of study drug
- General or specific changes in the patient's condition render the patient unacceptable for further treatment in the judgment of the investigator
- Suspected pregnancy
- Serious non-compliance with the study protocol
- Lost to follow-up
- Patient withdraws consent
- Investigator removes the patient from study
- The Siteman Cancer Center decides to close the study

Patients who prematurely discontinue treatment for any reason will be followed as indicated in the study calendar.

5.4 Concomitant Therapy and Supportive Care Guidelines

5.4.1 Chemotherapy

Patients cannot receive any chemotherapy within 21 days of study enrollment and must have recovered from any treatment-related toxicities. However, patients may be receiving hydra at enrollment and may continue on hydra through Cycle 2 of decitabine. An indication for hydra following 2 cycles of decitabine is evidence

that the patient is not responding and decitabine should be discontinued. Other than decitabine, patients cannot receive chemotherapy during this trial.

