1.3 Correlative Studies

All correlative studies will be collected under HRPO# 201011766 (“Tissue Acquisition for Analysis of Genetic Progression Factors in Hematologic Diseases”) that all patients will be concurrently enrolled in. The goals of the correlative studies include:

1. To correlate patient-specific mutations with response to decitabine.
We will perform exome sequencing of each patient’s pre-study bone marrow sample and skin sample. We will determine AML/MDS-associated variants found in the bone marrow, but not skin sample. We will correlate the presence of mutations with response (especially mutations in *DNMT3A*, *IDH1*, *IDH2*, and *TET2*). This study is powered to identify mutations with >80% sensitivity to predict decitabine response if used as a clinical assay.
2. To correlate the velocity and depth of response with response to decitabine.
We will assess tumor burden by allele frequency of patient-specific mutations in bone marrow samples collected pre study, Cycle 1 Day 10±1, Cycle 1 Day 28±4, and Cycle 2 Day 28±4. We will assess mutations in at least 24 recurrently mutated genes (including, but not limited to: *FLT3*, *DNMT3A*, *NPM1*, *TET2*, *WT1*, *IDH1*, *IDH2*, *RUNX1*, *NRAS*, *TP53*, *U2AF1*, *KRAS*, *PHF6*, *MSTP9*, *PTPN11*, *KIT*, *SMC3*, *PRUNE2*, *ETV6*, *CEBPA*, *SMC1A*, *ASXL1*, *STAG2*, *RAD21*) as well as all patient-specific mutations discovered during exome sequencing. The leukemic allele frequency will be measured using the Illumina MySeq or HiSeq platform using DNA capture by gene specific biotinylated-oligonucleotides. Patient bone marrow samples will be assessed pre-study, Cycle 1 Day 10 ± 1, Cycle 1 Day 28 ± 4, and Cycle 2 Day 28 ± 4 and compared with patient specific skin samples (normal control). The velocity of response will be calculated as the natural log rate of patient-specific mutation allele frequency clearance. Depth of response will be defined as the lowest patient-specific mutation

allele frequency in a bone marrow sample. The velocity and depth of tumor response will be correlated to:

- Achievement of clinical CR,
- Time to best response,
- Mutational status,
- Time to disease progression.

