5.4 Concomitant Therapy and Supportive Care Guidelines

5.4.1 Chemotherapy

Patients cannot receive any chemotherapy within 21 days of study enrollment and must have recovered from any treatment-related toxicities. However, patients may be receiving hydrea at enrollment and may continue on hydrea through Cycle 2 of decitabine. An indication for hydrea following 2 cycles of decitabine is evidence that the patient is not responding and decitabine should be discontinued. Other than decitabine, patients cannot receive chemotherapy during this trial.

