14.2.3 Secondary Endpoint Analyses

The overall response rate (CR/CRi/PR) and complete response rate (CR/CRi) will be compared with historical controls[2], and the 95% confidence intervals will be provided.

The rate of patient specific mutation clearance after 10, 28, and 56 days of therapy will be determined using an Illumina based platform. We will compare the rate of mutation clearance between the patients who achieve a CR/CRi after 4 cycles and those who do not. We anticipate that we will identify between 6 and 25 exonic SNVs per case (the range obtained with >200 AML samples sequenced to date with whole genome or exome sequencing), and that the expected 95% confidence interval of the mean variant allele frequency will be $\pm 2.56\%$ and $\pm 1.25\%$,

respectively, if we assume an anticipated standard deviation of 3.2% within the same clone. The change of tumor burden over time and its association with clinical response will be assessed using 2-way ANOVA for repeated measurement data, followed by the ad-hoc multiple comparisons for between-group differences (e.g., responders vs. non-responders) at given time points as well as the between-time differences within each group. The resultant critical P values will also be corrected using permutation analysis for multiple testing.

The percent decrease in bone marrow methylcytosine will be calculated on day 10 ± 1 . We will compare this reduction with previously published data and between the patients who achieve CR/CRi and those who do not. The correlation of peak plasma levels of decitabine with response will be assessed using 2-sample t-test or Mann-Whitney non-parametric rank-sum test as appropriate. The change of total bone marrow DNA methylcytosine from baseline and its association with both steady-state plasma drug levels and response will be assessed using 2-way ANOVA for repeated measurement data, followed by the ad-hoc multiple comparisons for between-group differences (e.g., responders vs. non-responders) and between-time differences. Similar analyses will be performed for the correlation of expression profiles and SNP analysis with pharmacokinetic data.

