14.2.3 Secondary Endpoint Analyses

The overall response rate (CR/CRi/PR) and complete response rate (CR/CRi) will be compared with historical controls[2], and the 95% confidence intervals will be provided.

The rate of patient specific mutation clearance after 10, 28, and 56 days of therapy will be determined using an Illumina based platform. We will compare the rate of mutation clearance between the patients who achieve a CR/CRi after 4 cycles and those who do not. We anticipate that we will identify between 6 and 25 exonic SNVs per case (the range obtained with >200 AML samples sequenced to date with whole genome or exome sequencing), and that the expected 95% confidence interval of the mean variant allele frequency will be $\pm 2.56\%$ and $\pm 1.25\%$,

respectively, if we assume an anticipated standard deviation of 3.2% within the same clone. The change of tumor burden over time and its association with clinical response will be assessed using 2-way ANOVA for repeated measurement data, followed by the ad-hoc multiple comparisons for between-group differences (e.g., responders vs. non-responders) at given time points as well as the between-time differences within each group. The resultant critical P values will also be corrected using permutation analysis for multiple testing.

The percent decrease in bone marrow methylcytosine will be calculated on day 10 ± 1 . We will compare this reduction with previously published data and between the patients who achieve CR/CRi and those who do not. The correlation of peak plasma levels of decitabine with response will be assessed using 2-sample t-test or Mann-Whitney non-parametric rank-sum test as appropriate. The change of total bone marrow DNA methylcytosine from baseline and its association with both steady-state plasma drug levels and response will be assessed using 2-way ANOVA for repeated measurement data, followed by the ad-hoc multiple comparisons for between-group differences (e.g., responders vs. non-responders) and between-time differences. Similar analyses will be performed for the correlation of expression profiles and SNP analysis with pharmacokinetic data.

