9.1 Response Criteria - AML

AML Patients will be assessed for response according to the IWG criteria:¹

Morphologic complete remission (CR) – Defined as morphologic leukemia-free state, defined as less than 5% blasts in aspirate with marrow spicules and a count of ≥ 200 nucleated cells and no blasts with Auer rods or any persistence of extramedullary disease. When erythroid precursors constitute less than 50% of bone marrow nucleated cells, the percentage of blasts is based on all nucleated cells; when there are 50% or more erythroid cells, the percentage blasts should be based on the nonerythroid cells. The presence of mild megaloblastoid changes may be permitted if they are thought to be consistent with treatment effect. However, persistence of pretreatment abnormalities (eg, pseudo-Pelger-Huet cells, ringed sideroblasts, dysplastic megakaryocytes) are not consistent with CR. In addition, ANC $> 1000/\mu\text{l}$ and platelet count of $\geq 100,000/\mu\text{l}$. Patient must be independent of transfusions. No duration requirement for this designation.

Cytogenetic complete remission (CCR) – Defined as morphologic complete remission plus a reversion to a normal karyotype. For this study, reversion of a normal karyotype is defined as no clonal abnormalities detected in a minimum of 20 mitotic cells.

Morphologic complete remission with incomplete blood count recovery (CRi) – Defined as morphologic complete recovery with the exception of neutropenia $< 1000/\mu\text{l}$ or thrombocytopenia $< 100,000/\mu\text{l}$.

Partial remission (PR) – Defined as meeting the above criteria for complete remission, with the following exceptions: decrease of $\geq 50\%$ in the percentage of blast to 5-25% in the bone marrow aspirate. A value of $\leq 5\%$ blasts in bone marrow with Auer rods present may also be considered a partial remission.

Stable Disease (SD) – Defined as not meeting the definitions of CR, CRi, PR, PD, or recurrence/morphologic relapse.

Progressive disease (PD) – Defined as a clear increase in bone marrow blast count, typically a greater than 50% increase compared with baseline, or new extramedullary disease. Patients with a $> 50\%$ increase in peripheral blast count with an increase of the total peripheral white blood cell count to $> 10,000/\mu\text{l}$ should undergo evaluation by bone marrow biopsy to access for progressive disease.

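### Hydroxyurea is allowed throughout the window in which mutation clearance and methylcytosine loss are measured, but no planned analysis or listed form title covers it, so possible confounding cannot be examined

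*Combined protocol and SAP*

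**What the plan says.** The file holds several copies of the protocol. They agree on this point, and references below are to the copy printed first.

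- **Permission.** Section 5.4.1 states that "patients may be receiving hydrea at enrollment and may continue on hydrea through Cycle 2 of decitabine". Another copy has the same rule with the drug's name spelled differently: "patients may be receiving hydra at enrollment and may continue on hydra through Cycle 2 of decitabine". The sentence is an exception within the section on chemotherapy, which otherwise allows only decitabine.
- **Link to outcome.** The same section adds: "An indication for hydrea following 2 cycles of decitabine is evidence that the patient is not responding", and says decitabine should then be stopped.
- **Clearance samples.** Section 1.3 has marrow "assessed pre-study, Cycle 1 Day 10 ± 1, Cycle 1 Day 28 ± 4, and Cycle 2 Day 28 ± 4". Section 14.2.3 states: "The rate of patient specific mutation clearance after 10, 28, and 56 days of therapy will be determined".
- **Clearance metric.** Section 1.3: "The velocity of response will be calculated as the natural log rate of patient-specific mutation allele frequency clearance".
- **Methylcytosine.** Sections 1.3 and 14.2.3 measure the percent reduction from pre-study to Cycle 1 Day 10. Section 1.3 says this will show whether too little exposure of blasts to decitabine goes with resistance.
- **Analysis.** Section 14.2.3 uses repeated-measures ANOVA and two-group comparisons by response. It also compares methylcytosine loss with published data. Hydroxyurea is not mentioned there or among the subgroups of Section 14.2.5. The only covariate adjustment is the logistic model of Section 14.2.2, for unnamed demographic and clinical characteristics.
- **Data capture.** No form title in Section 15.0 refers to concomitant therapy.
- **Event-free survival.** Section 9.4.1 defines treatment failure as no complete or partial remission after 4 cycles. The other events are recurrence, death and loss to follow-up.

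**The concern.** A second drug that the protocol itself groups with chemotherapy may be given during the whole period in which the secondary biomarkers are measured. Whether a patient is on it could be related to the disease at entry, and so to response. If it also affects allele frequency or methylcytosine, the responder versus non-responder comparison mixes the two drugs. The comparison with published data is exposed even if use is the same in both response groups. At stake is the interpretation: the plan reads these markers as measures of what decitabine did, and it specifies neither the data nor the analysis needed to check that.

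A separate difficulty concerns event dating. Section 5.4.1 can label a patient non-responding after Cycle 2 and end decitabine, while Section 9.4.1 recognises failure only after four cycles.

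**Working it through.** **1. Does the permitted period cover the samples?** Cycles are 28 days, so Cycle 2 nominally ends on Day 28 + 28 = 56. Clearance samples are at Days 10, 28 and 56, and methylcytosine at Day 10. All nominal on-treatment time points lie inside the period. The ±4-day window lets the last marrow fall slightly later, which does not change the point.

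**2. The plan's own power figures (Section 14.2.3).**
- Methylcytosine: difference 20, SD 15, 45 versus 55 patients, two-sided 0.05. Standard error = 15 × √(1/45 + 1/55) = 3.015, and 20/3.015 = 6.63. Power exceeds 99.9%, so the stated 99% is met.
- Clearance, two-sample t-test with n variants at each of two time points: n = 6 and 10 points give 99.8% (SD 3.2) and 91.2% (SD 4.7); n = 3 and 15 points give 98.6% and 82.8%. The stated figures are above 99%, 91%, above 98% and 82%, so all four reproduce.

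The clearance calculation compares time points within one clone. It says nothing about responders versus non-responders.

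**3. What would have to be true for bias?** Allele frequency is mutant reads over total reads, m/(m + w). If a drug removes the same fraction of both, leaving a share k, then km/(km + kw) = m/(m + w), and nothing changes. Percent methylcytosine is likewise a proportion. Bias needs a selective effect on the clone or on methylated DNA, and the documents do not say whether hydroxyurea has one.

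**4. Sensitivity of the methylcytosine difference, on assumed values only.** Let hydroxyurea add c points of apparent reduction in a share hN of non-responders and hR of responders. The difference becomes 20 − (hN − hR) × c, and the variance in each group becomes 15² + h(1 − h)c². None of hN, hR or c is in the documents.

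| hN / hR | c | Difference | Power |
|---|---|---|---|
| equal, 10% to 30% | −10 to 20 | 20 | at least 99.99% |
| 20% / 5% | 10 | 20 − 0.15 × 10 = 18.5 | above 99.9% |
| 40% / 10% | 10 | 20 − 0.30 × 10 = 17.0 | 99.98% |
| 40% / 10% | 20 | 20 − 0.30 × 20 = 14.0 | 98.4% |
| 60% / 10% | 20 | 20 − 0.50 × 20 = 10.0 | 83% |
| 40% / 10% | −10 | 20 + 0.30 × 10 = 23.0 | above 99.9% |
| 60% / 10% | −10 | 20 + 0.50 × 10 = 25.0 | above 99.9% |

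With SD 15 throughout, power falls to 99% only at a difference of about 13 points and to 80% at about 8.5.

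**5. Comparison with published data.** Equal use does not cancel here. A share h shifts the study mean by h × c: with c = 10, from 0.10 × 10 = 1 point to 0.30 × 10 = 3 points, and by the same amounts the other way with c = −10. This assumes that the published patients were not similarly exposed, which the documents do not state.

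**6. Event-free survival.** Take a patient who never remits and is taken off decitabine after Cycle 2 under Section 5.4.1. Four cycles were not given, so treatment failure as defined has no date. Recurrence presupposes a remission. Only death or loss to follow-up remains as a dated event, although the protocol has already judged the patient non-responding.

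**The case against.** The strongest reply is that no bias has been shown. The sentence tying hydroxyurea to non-response concerns a need for it after Cycle 2, which is after the biomarker samples. No usage rate or marker effect is given, both markers are proportions, and methylcytosine power holds up in all but extreme scenarios. This stands. A reader might infer that hydroxyurea's cytoreduction is credited to decitabine mainly in non-responders; the documents do not support that direction. Nor can any assumed shift be set against the 10-point clearance difference, which is a within-clone comparison of time points.

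It can also be said that Section 15.0 lists form titles, not fields. Exclusion criterion 9 mentions hydroxyurea at enrolment, so the exclusion worksheet may note it, and reasons for discontinuation are documented. That stands too: the exact statement is that no title covers concomitant therapy and nothing in the plan requires dates. Transfusions, by contrast, are recorded from 8 weeks before the first dose onward.

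For the primary endpoint, the logistic model could already include hydroxyurea. It simply does not name it.

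Two further inferences fail. One is that hydroxyurea hides progression by holding down the white count in Section 9.1. That criterion ("with an increase of the total peripheral white blood cell count to" a threshold, together with rising peripheral blasts) only prompts a marrow, and marrows are scheduled at Day 28 of Cycles 1 and 2 anyway. The other is that a patient stopped for hydroxyurea need must be stable disease; the Cycle 2 and end-of-study marrows may show something else.

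What the reply does not answer is that unknown direction is a reason to collect the data.

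**Conclusion.** The point holds as a gap in the secondary biomarker analyses. Hydroxyurea is permitted across the whole measurement window, the comparisons by response and with published data ignore it, and the listed forms are not shown to capture it. Confounding of unknown size and direction therefore cannot be examined, while the results are to be interpreted as decitabine effects. The scenario table shows how the methylcytosine difference would respond to assumed inputs; it does not estimate bias. For clearance the plan gives no between-group figure against which to set any effect. The primary analysis is touched only in that its covariates are unnamed.

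The mismatch between Sections 5.4.1 and 9.4.1 rests on the text alone and needs no assumption about hydroxyurea's effect. Whether hydroxyurea should be allowed is not at issue.

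**What to change.** 1. Record hydroxyurea at entry (yes/no) and its start and stop dates on the Treatment Record Form.
2. Add hydroxyurea at entry as a factor in the clearance and methylcytosine comparisons of Section 14.2.3, and name it among the clinical covariates in Section 14.2.2. Use at entry precedes treatment, so it is a proper adjustment variable.
3. Repeat both comparisons, and the methylcytosine comparison with published data, without exposed patients. Label this a sensitivity analysis, since continued use is determined after baseline.
4. Reconcile Section 5.4.1 with Section 9.4.1. For event-free survival, count discontinuation as non-responding after Cycle 2 as treatment failure on that date. This is a rule for dating the endpoint and leaves the stopping of treatment as it is.

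The cost is a small addition to one form, one covariate and a smaller sample in the sensitivity analysis. Patient care does not change.
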